Patients actively receiving therapy may be considered for intra-patient dose escalation to receive a dose level no higher than the highest dose that has previously been deemed safe and tolerable (and thus below the MTD) by the CRC, following review and approval by the Medical Monitor ([Section 3.1.1.4](#)).

During Dose Expansion, up to 20 additional evaluable patients will receive HPN424 at the RP2D(s) established in the Dose Escalation stage of the study.

HPN424 will be administered by either intravenous (IV) infusion or subcutaneous (SC) injection. All patients will be administered HPN424 once weekly (QW) during 21-day cycles. Pre-medications will be administered as indicated based on assigned cohort ([Section 5.1.4](#)).

Patients may continue to receive HPN424 treatment beyond disease progression provided there is clinical benefit (NLCB, per PCWG3 guidelines, ([Scher, 2016](#)) as determined by the Investigator and upon consultation with the Medical Monitor. Disease assessments (PSA, bone scans and CT/MRI) should continue irrespective of whether study treatment is missed or delayed.

3.1.1 *Part 1: Dose Escalation Study Design*

Dose escalation will be performed initially with single patient cohorts followed by a 3 + 3 design with two parallel arms (Fixed Dosing, Step Dosing) to evaluate tolerability of different dosing regimens:

- During single patient dose escalation and in the 3 + 3 dose escalation Fixed Dosing arm, patients will receive the Target Dose (the intended dose for a particular cohort) starting on Cycle 1 Day 1 and beyond.
- During step dosing, patients will initiate treatment with Priming Dose A on Cycle 1 Day 1. The Target Dose will be administered on Cycle 1 Day 8 and beyond.

- A second priming dose, Priming Dose B, may be implemented in the next cohort on Cycle 1 Day 8. In this case, the Target Dose will be administered on Cycle 1 Day 15 and beyond ([Section 3.1.1.2.2](#)).
- Additional Priming Doses may be added (e.g., Priming Dose C) based on the observed safety and tolerability ([Section 3.1.1.2.2](#)).

For safety reasons, a staggered start will be employed when a higher dose level cohort is opened. At least 48 hours must elapse between dosing of the first and second patient at any given dose level.

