5.1.4.2 Step Dosing Regimen

For patients enrolled in the Step Dosing regimen, hospitalization is as follows:

- Priming Dose(s): Hospitalized a minimum of 48 hours after the administration of each Priming Dose.
 - If the patient experiences signs or symptoms of CRS/IRR, hospitalization may be extended for monitoring beyond 48 hours until it is confirmed that the patient is symptom free and is stable for discharge.
 - After at least 6 patients have initiated treatment with a given priming dose, duration of hospitalization for that priming dose or lower priming dose levels may be reduced or omitted based on CRC review of the safety data.
 - If hospitalization is omitted, observation following first administration of a Priming Dose will be for at least 6 hours after study drug administration.

In the outpatient setting, if the patient experiences signs or symptoms of CRS/IRR, post dose monitoring should be extended until it is confirmed that the patient is symptom free for at least one hour and confirmed by the treating physician that the patient is stable for discharge.

- Target Dose(s): Hospitalized a minimum of 48 hours after the administration of the first 2 Target Doses.
 - If the patient experiences signs or symptoms of CRS/IRR, hospitalization may be extended for monitoring beyond 48 hours until it is confirmed that the patient is symptom free and is stable for discharge.
 - If the first 2 Target Doses have been well tolerated, subsequent doses of HPN424 may be administered on an outpatient basis. During subsequent Target Doses through Cycle 3, patients are to remain in the clinic for safety monitoring for at least 4 hours after each administration. Beginning with Cycle 4 and beyond, the observation period may be reduced to no less than 2 hours after administration.

Based on emergent safety data and review by the CRC, duration of hospitalization for the first and/or second Target Dose(s) may be reduced or omitted. If hospitalization is omitted, outpatient observation following the administration of the first 2 Target Doses will be for at least 6 hours after the study drug administration.

In the outpatient setting, if the patient experiences signs or symptoms of CRS/IRR, post dose monitoring should be extended until it is confirmed that the patient is symptom free for at least an hour and confirmed by the treating physician that the patient is stable for discharge.

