8.2 Treatment Period

Cycle 1 Day 1 predose assessments must be completed within 72 hours prior to the start of the Cycle 1 Day 1 dose of HPN424, unless otherwise indicated. If screening assessments were done within this window, they need not be repeated on Cycle 1 Day 1.

The timing of dose administration, hospitalization schedule ([Section 5.1.4](#)), and DLT observation period for each cohort is dependent on the assigned dosing regimen and treatment arm and detailed in [Table 15](#).

Table 15 Cycle 1 Treatment and Monitoring Schedule

	Fixed Dose Regimen	One Priming Dose Regimen (Prime A)	Two Priming Dose Regimen (Prime A + Prime B)	Three Priming Dose Regimen (Prime A + Prime B + Prime C) ^b
Priming Dose A	--	C1D1	C1D1	C1D1
Priming Dose B	--	--	C1D8	C1D8
Priming Dose C	--	--	--	C1D15
Target Dose	C1D1	C1D8	C1D15	C2D1
DLT Period	D1-D21	D1-D28	D1-D35	D1- D42
Hospitalization	C1D1, C1D8	C1D1 ^a , C1D8, C1D15	C1D1 ^a , C1D8 ^a , C1D15, C2D1	C1D1 ^a , C1D8 ^a , C1D15, C2D1, C2D8

^a Hospitalization for Priming and Target dose(s) may be reduced or omitted based on CRC review of the emergent safety data at a particular dose level (Section 5.1.4).

^b If additional Prime Doses are added (e.g., Prime Dose D) Cycle/Day for Prime Dose and first Target dose will be determined by the number of Priming doses for a given regimen (e.g., Priming Dose A will be administered on C1D1, Priming Dose B on C1D8, Priming Dose C on C1D15, and Priming Dose D on C2D1 and so on. The DLT period for all patients in a given cohort will be through 21 days after the first Target Dose.

The patient will be asked to complete scheduled visits and assessments per assigned dose regimen.

During the Treatment Period, disease assessments (including PSA and radiological imaging) are to be performed as indicated irrespective of whether treatment is delayed or missed. In other words, the schedule for these items is calendar-based and fixed relative to C1D1.

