- ^a Long-term follow-up telephone calls or visits to occur monthly (± 7 d) for 6 months, then every 3 months (± 1 month) until death, lost to follow-up, or withdrawal from study.
- ^b Predose assessments are to be done on the day of, and prior to, the start of infusion, unless otherwise indicated. C1D1 predose assessment must be completed within 72 hours prior to start of the C1D1 dose of HPN424, unless otherwise indicated. If Screening assessments were not done within this window, they need to be repeated on C1D1. C1D8+ predose assessments may be completed within 24 hours prior to the start of HPN424 infusion, provided it is after the previous dose.
- ^c Hospital admission: 48-hour inpatient admission required following C1D1 and C1D8 dosing for all patients treated at each specific dose level. All patients who undergo intrapatient dose escalation will be hospitalized for 24-hour inpatient observation following the first of each escalated dose. Please refer to [Section 5.1.4 Hospitalization and Monitoring](#) for additional instruction on requirements for hospitalization.
- ^d Informed Consent form must be signed before any study-related procedures are performed.
- ^e Height is measured at Screening only.
- ^f Full physical examination at Screening; symptom-directed exams at indicated visits thereafter.
- ^g Vital signs: blood pressure, heart rate, respiratory rate, and temperature at the following timepoints during treatment, or more often if clinically indicated: during each HPN424 dose, predose (within 1 hour prior to the start of infusion), every 15 minutes (± 10 min) during the infusion (i.e., 15, 30, 45, 60 minutes), and at 4 hours (± 1 h) after the end of infusion (EOI). For inpatients at C1D1, vital signs are to be recorded every 4 hours (± 1 h) until discharge. Beginning with Cycle 4 and beyond, the Investigator may have the option to reduce the observation period from 4 hours to ≥ 2 hours after EOI. If the observation period is reduced to ≥ 2 hours, collect vital signs 2 hours (± 30 minutes) after EOI.
- ^h Hematology: complete blood count (CBC), including platelet count and white blood cell count (WBC) with differential. C1D1 samples to be collected within 72 hours prior to dose. C1D8+ samples to be collected within 24 hours prior to dose.

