- ^r CT/MRI imaging may include chest, abdomen, and pelvis CT or MRI scans (the same method should be used throughout the study). Brain scans will be performed at baseline if disease is suspected and on study as appropriate to follow disease. CT or MRI scans to be done every 9 weeks (± 7 days) (e.g., Day 1 of Cycles 4, 7, 10, 13, etc.). Tumor assessments should be repeated at the EOT visit if more than 9 weeks have passed since the last evaluation. Patients should have confirmatory scans for response or progression and should remain on treatment if they are receiving clinical benefit (as determined by the Principal Investigator and upon consultation with the Medical Monitor).
- ^s PSMA PET to be performed at selected sites only.
- ^t HPN424 IV will be administered via 1-hour infusion. HPN424 will be administered once weekly (-2 days/+1 day) with a minimum of 4 non-dose days between 2 consecutive doses. Doses are to be calculated based on the patient's baseline (Screening) body weight, not adjusted each cycle for weight at Day 1 of each cycle. Please refer to [Section 5.1.4 Hospitalization and Monitoring](#) for additional instruction on requirements for post-dose monitoring.
- ^u Adverse events (including serious AEs [SAEs]) recorded from signing of informed consent form through the SFU (≥ 28 days [+7 days] after last dose of HPN424).

- ^v C-reactive protein (CRP): at C1D1—predose (-72 h), 5 h (\pm 1 h) after end of infusion (EOI), C1D2—24 h (\pm 1 h) after EOI; C1D8—predose (-24 h); once per cycle (predose [- 24 h] starting with Cycle 2), and when signs of cytokine release syndrome (CRS) are observed.
- ^w 12-Lead ECG: Patients should be resting in a supine or sitting position for \geq 10 minutes prior to electrocardiogram (ECG) collection. Obtain 1 ECG pre-dose at each of the following timepoints: Screening; D1 of each cycle; EOT visit. If cardiac abnormalities are detected or suspected, two additional ECGs must be performed to further evaluate and each reading should be obtained at least 3 minutes apart.
- ^x Pulse oximetry: Within 1 hour prior to each dose.

Table 16 Intravenous Fixed Dosing Regimen: Research Specimen Collection

Cycle	Study Day	Cytokines ^a	Immuno-phenotyping	CTC	PK ^b	Anti-Drug Antibodies
Cycle 1	C1D1-Pre dose	X	X	X	X	X
	C1D1-EOI				X	
	C1D1-2 h Post EOI				X	
	C1D1-5 h Post EOI	X	X		X	
	C1D2	X	X		X	
	C1D3	X	X		X	
	C1D5				X	
	C1D8-Pre dose	X			X	
	C1D8-EOI				X	
	C1D8-5 h Post EOI	X			X	
	C1D15-Pre dose	X		X	X	X
	C1D15-EOI				X	

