- ^b Predose assessments are to be done on the day of, and prior to, the start of infusion, unless otherwise indicated. C1D1 predose assessment must be completed within 72 hours prior to start of the C1D1 dose of HPN424, unless otherwise indicated. If Screening assessments were not done within this window, they need to be repeated on C1D1. C1D8+ predose assessments may be completed within 24 hours prior to the start of HPN424 infusion, provided it is after the previous dose.
- ^c Hospital admission: Please refer to [section 5.1.4](#) Hospitalization and Monitoring for additional instruction on requirements for hospitalization and outpatient monitoring.
- ^d Informed Consent form must be signed before any study-related procedures are performed.
- ^e Height is measured at Screening only.
- ^f Full physical examination at Screening; symptom-directed exams at indicated visits thereafter.
- ^g Vital signs: blood pressure, heart rate, respiratory rate, and temperature at the following timepoints during treatment, or more often if clinically indicated: during each HPN424 dose, predose (within 1 hour prior to the start of infusion), every 15 minutes (± 10 min) during the infusion (i.e., 15, 30, 45, 60 minutes), and at 4 hours (± 1 h) after the end of infusion (EOI). For inpatients at C1D1 and C1D8, vital signs are to be recorded every 4 hours (± 1 h) until discharge. Beginning with Cycle 4 and beyond, the Investigator may have the option to reduce the observation period from 4 hours to ≥ 2 hours after EOI. If the observation period is reduced to ≥ 2 hours, collect vital signs 2 hours (± 30 minutes) after EOI.
- ^h Hematology: complete blood count (CBC), including platelet count and white blood cell count (WBC) with differential. C1D1 samples to be collected within 72 hours prior to HPN424 administration. C1D8+ samples to be collected within 24 hours prior to HPN424 administration. During 48-hour inpatient hospitalization, should be drawn once within 24-hour period after HPN424 administration, and once during 24-48-hour period after HPN424 administration.

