- ^q Bone scan: ^{99m}Tc-methylene diphosphonate radionuclide bone scintigraphy every 9 weeks (± 7 days) (e.g., Day 1 of Cycles 4, 7, 10, 13, etc.). Changes in lesions considered metastatic on bone scintigraphy should be followed and assessed serially using a bone scan assessment form [Appendix 7](#).
- ^r CT/MRI imaging may include chest, abdomen, and pelvis CT or MRI scans (the same method should be used throughout the study). Brain scans and bone scans will be performed at baseline if disease is suspected and on study as appropriate to follow disease. CT or MRI scans to be done every 9 weeks (± 7 days) (e.g., Day 1 of Cycles 4, 7, 10, 13, etc.). Tumor assessments should be repeated at the EOT visit if more than 9 weeks have passed since the last evaluation. Patients should have confirmatory scans for response or progression and should remain on treatment if they are receiving clinical benefit (as determined by the Principal Investigator and upon consultation with the Medical Monitor).
- ^s PSMA PET to be performed at selected sites only.

- ^t HPN424 IV will be administered via 1-hour infusion. HPN424 will be administered once weekly (-2 days/+1 day with a minimum of 4 non-dose days between 2 consecutive doses) as a 1-hour infusion. Doses of HPN424 are to be calculated based on the patient's baseline (Screening) body weight, not adjusted each cycle for weight at Day 1 of each cycle. Please refer to [section 5.1.4 Hospitalization and Monitoring](#) for additional instruction on requirements for post-dose monitoring.
- ^u Adverse events (including serious AEs [SAEs]) recorded from signing of informed consent form through the SFU (≥ 28 days [$+7$ days] after last dose of HPN424).
- ^v C-reactive protein (CRP): at C1D1—predose (-72 h), 5 h (± 1 h) after HPN424 administration; C1D2— 24 h (± 1 h) after HPN424 administration; C1D8—predose (-72 h), 5 h (± 1 h) after HPN424 administration; C1D9— 24 h (± 1 h) after HPN424 administration; once per cycle (predose [$- 24$ h] beginning with first Target dose), and when signs of cytokine release syndrome (CRS) are observed

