- ^b Cytokine Samples: If more than one priming dose is required and the target dose is after C1D8, do not collect cytokine samples on C1D9; At first target dose, collect samples predose, 5 h (\pm 1 h) post EOI and 24 h (\pm 1 h) post EOI. Serum specimens will be collected during treatment if signs of CRS or neurotoxicity are observed. Additional serum samples may be collected as needed (e.g., following CRS, Grade \geq 3 IRR, HPN424 dose modification, dose schedule modification, steroid [i.e., dexamethasone] use/dose modification, etc.). If CRS occurs (or is observed, regardless of the grade), the site should draw a cytokine panel (specifically IL-6) using their local lab or the central laboratory.
- ^c Immunophenotyping samples: If more than one priming dose is required and the target dose is after C1D8, do not collect immunophenotyping samples on C1D9 nor C1D10. At first target dose, collect samples predose, 5 h (\pm 1 h) post EOI, 24 h (\pm 1 h) post EOI, and 48 h (\pm 1 h) post EOI.
- ^d CTC samples: Collected at C1D1, and 2, 13, and 24 weeks after the first target dose. For example, if first target dose is C1D8, follow collection in table. If first target dose is C1D15, draw CTCs at C2D8, C6D1, and C9D15. Sample on C3D1 should always be collected regardless of when the first target dose occurs.
- ^e PK Samples: If more than one priming dose is required and the target dose is after C1D8, do not collect PK samples on C1D9, C1D10, nor C1D12. At first target dose, collect samples predose, within 15 minutes after EOI, 2 h (\pm 1 h) post EOI, 5 h (\pm 1 h) post EOI, 24 h (\pm 1 h) post EOI, 48 h (\pm 1 h) post EOI, and 96 h (\pm 24 h) post EOI. The 96 hour timepoint will require subjects to return to clinic for PK blood draw. Additional serum samples may be collected as needed (e.g., following CRS, Grade \geq 3 IRR, HPN424 dose modification, dose schedule modification, steroid [i.e., dexamethasone] use/dose modification, etc.).

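### With two priming doses, the step-dosing schedule gives the first Target Dose neither 4-hourly inpatient vital signs nor a scheduled post-dose CRP

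*Protocol*

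**What the plan says.** Appendix 2 of the protocol covers IV step dosing. Its footnote g sets a routine for every dose: one set of vital signs beforehand, one every 15 minutes of the infusion, and one at 4 h (± 1 h) after it ends, with extra readings on clinical judgement. It then adds an inpatient rule tied to calendar days: "For inpatients at C1D1 and C1D8, vital signs are to be recorded every 4 hours".

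Footnote v schedules CRP before, 5 h after and 24 h after the C1D1 and C1D8 doses. Beyond those it asks for one predose sample per cycle, "beginning with first Target dose), and when signs of cytokine release syndrome (CRS) are observed". Appendix 4 (SC step dosing) has the same two day rules.

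When Priming Dose B is given on C1D8, section 3.1.1 says: "In this case, the Target Dose will be administered on Cycle 1 Day 15 and beyond". Table 15 in section 8.2 agrees. Section 5.1.4.2 sets the stay: "Hospitalized a minimum of 48 hours after the administration of the first 2 Target Doses". The stay is not absolute; a note to Table 15 says "Hospitalization for Priming and Target dose(s) may be reduced or omitted based on CRC review of the emergent safety data".

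**The concern.** Footnotes g and v follow the calendar, while the first Target Dose moves with the number of primes. They fit a one-prime regimen, where that dose is on C1D8. With two primes they cover the two lower doses and miss the Target Dose.

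Appendix 8 wants action as soon as CRS shows itself, and names fever, fast heart rate, fast breathing and low blood pressure as early signs. Footnote g schedules exactly these measurements. Section 3.1.1.2.2 lets the CRC add Priming Dose B after Grade 2 or worse CRS at a Target Dose, so a regimen brought in because of CRS at the Target Dose loses scheduled CRS monitoring there. Under the grading in Appendix 8, fever with hypotension that needs no vasopressor is already Grade 2, and Grade 2 CRS drives priming decisions. The frequency of temperature and blood pressure readings therefore bears on them.

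**Working it through.** The plan states no figure on this point. The check sets each regimen's first Target Dose against its own schedule, then counts mandated recordings.

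**1. Coverage at the first Target Dose, by SAP group (SAP section 7.1)**

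| Group | First Target Dose | 4-hourly inpatient vital signs | 5 h and 24 h CRP |
|---|---|---|---|
| Fixed IV (Appendix 1) | C1D1 | yes: "For inpatients at C1D1, vital signs are to be recorded every 4 hours" | yes: 5 h "after end of infusion (EOI), C1D2—24 h" |
| Fixed SC (Appendix 3) | C1D1 | yes, same rule | yes |
| One-prime step IV (Appendix 2) | C1D8 | yes | yes |
| Two-prime step IV (Appendix 2) | C1D15 | no | no |

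Three of four groups have both items; the two-prime group has neither.

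**2. Does another section fill the gap?** None found. Section 5.1.4.2 fixes the stay but no recording interval. Section 5.4.1 requires regular monitoring during the infusion, and CRP if CRS occurs. Section 6.6 gives no times. Table 12 in section 6.9 refers CRP timing back to the schedules. The Appendix 2 grid may mark CRP at C1D15 (its columns are broken in the extracted text), but footnote v permits only a predose sample there.

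**3. What other assessments do in Appendix 2.** Cytokine, immunophenotyping and PK sampling moves with the dose (Table 17 footnotes: "At first target dose, collect samples predose"). Inpatient hematology and chemistry follow the stay. The extra liver tests in footnote i already name C1D15.

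**4. Mandated recordings at an IV first Target Dose on C1D15**

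- Post-infusion sets, 48-hour stay: 48 / 4 = 12 under the 4-hourly rule, against 1 as written; difference 11.
- All sets, adding 1 predose and 4 during the infusion: 1 + 4 + 12 = 17, against 1 + 4 + 1 = 6.
- Part of the stay after the last mandated set: 48 − 4 = 44 h (48 − 5 = 43 to 48 − 3 = 45 with the ± 1 h window).
- Stay cut to 24 h (assumed example): 24 / 4 = 6 against 1, or 1 + 4 + 6 = 11 against 6 in all.
- Stay omitted: no difference in vital signs.
- Scheduled post-dose CRP: 2 (5 h and 24 h) against 0.

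**5. Primes plus first Target Dose covered by footnotes g and v**

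- One prime (C1D1, C1D8): 2 of 2.
- Two primes (C1D1, C1D8, C1D15): 2 of 3.
- Three primes (C1D1, C1D8, C1D15, C2D1): 2 of 4. Table 15 allows this regimen; the SAP lists no such cohort.

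**6. Dose steps in the two-prime cohorts (SAP section 7.1)**

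| Cohort | Prime A to Prime B (C1D8) | Prime B to Target (C1D15) |
|---|---|---|
| 501 | 300 / 100 = 3 | 450 / 300 = 1.5 |
| 502, 503 | 150 / 50 = 3 | 300 / 150 = 2 |
| 504 | 150 / 50 = 3 | 450 / 150 = 3 |

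The absolute dose is highest at C1D15 in every cohort.

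**The case against.** The literal reading is not in dispute. The case against it concerns importance and intent.

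- *Monitoring does not vanish at C1D15.* The routine set of readings applies, more can be taken on clinical judgement, and CRP is drawn if CRS is suspected. This stands: only the scheduled measures are missing. The same safeguards exist at C1D1 and C1D8, though, and a schedule was still fixed there.
- *The 4-hourly rule was never attached to every stay.* Fixed-dose patients stay after C1D8, and one-prime patients after C1D15, without it. Two-prime patients get it at two doses and fixed-dose patients at one. This is correct. The consistent pattern lies elsewhere: the other three groups have it at the first Target Dose.
- *The choice may be deliberate.* Section 3.2.4 reports that IL-6 release was greatest after the first dose. Section 5.4.3 places most high-grade transaminitis after the first dose or the first step-up. The C1D8 step is 3-fold in all four cohorts, at least as large in relative terms as the later one. Intent therefore cannot be established, and an oversight is only an inference. Against a deliberate choice, the only dose level section 3.2.4 names for this trial's data is 72 ng/kg, while two-prime Target Doses are 300 to 450 ng/kg.
- *Little would change in practice.* Grade 3 and 4 CRS are defined by interventions such as vasopressors or high-flow oxygen, which would be noticed anyway. Laboratory and cytokine samples are already taken during the stay. Appendix 8 itself says CRP tracks CRS only variably. This stands, and it makes CRP the weaker half of the point.
- *The study ended in Part 1, and the SAP lists no SC step cohort.* Both are true and limit the fix to later use.

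**Conclusion.** The point holds as a minor schedule defect. As written, a two-prime patient's first Target Dose lacks two scheduled CRS measures that the other three SAP groups have at theirs. Over a full 48-hour stay after an IV dose, the shortfall is 11 vital-sign sets and 2 CRP samples.

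The vital-sign figure assumes that the CRC has not shortened or omitted the stay, and all counts are of mandated recordings. The documents do not say which protocol version governed cohorts 501 to 504, so no effect on those patients is claimed. The SAP puts vital signs in a by-patient listing and assigns CRP no CTCAE grade, so no planned table changes.

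**What to change.** In Appendices 2 and 4, reword footnote g so that the 4-hourly rule applies to *inpatients after each Priming Dose and after the first Target Dose, whichever day it falls on*. Reword footnote v so that the 5 h and 24 h CRP draws follow the same doses. As an option, extend the extra liver tests in footnote i to a first Target Dose on C2D1.

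Cost per inpatient on the IV schedule:

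- One prime: nothing.
- Two primes: up to 11 extra vital-sign recordings and two CRP samples, taken with the 5 h and 24 h cytokine draws already required at the first Target Dose.
- Three primes: two uncovered doses (C1D15 and C2D1), so up to 2 × 11 = 22 recordings and 2 × 2 = 4 CRP samples, plus two liver samples if that option is taken.
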